#### 9.4.7 Patient-Reported Outcomes and Adverse Events

Safety and toxicity will be assessed by PROs and AEs (PRO-CTCAE) captured by digital instruments every 2 weeks through Week 28 for acute and long-term toxicity.

The PRO-CTCAE data will be evaluated for data quality, to evaluate the symptoms' changes over time on study, to explore the development of symptomatic AEs and the change over time, and to explore the patient scores with clinician graded AEs. PRO-CTCAE data will be summarized descriptively as the number (percent) of patients reporting each grade for individual items.

#### 9.4.8 Clinical Progression-Free Survival

Clinical PFS will be calculated from the time of study enrollment until disease progression, which is defined as 1) symptomatic progression (increasing pain from a metastatic lesion); 2) progression of bone lesions assessed per PCWG3 criteria; or 3) progression of soft-tissue lesions

assessed per RECIST v1.1 criteria. PSA progression without progression on bone lesions nor symptomatic is not considered as clinical progression. Clinical PFS will be censored if clinical progression is not observed.

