1.2.9 To evaluate progression-free survival (PFS) and overall survival (OS)

### 1.3 Exploratory Objectives

1.3.1 To examine any tumor genomic alterations that may be associated with response or resistance to Sn-117m-DTPA, a radiopharmaceutical agent.

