### 5.10.2.2.2 Timing of Assessment

Pain at baseline and analgesic use (pre-treatment, Week 0) will be measured via serial (daily) assessments in a 7-day run-in period. Patients will be considered evaluable if they complete assessments on  $\geq 4$  days within the 7-day run-in period. During treatment, pain and analgesic use will be measured every 2 weeks through Week 28, followed by routine clinic follow-up until 1 year or when patients experience new pain. Complete pain assessments via the full BPI-SF (Appendix D) will be collected at baseline, after Cycle 1, after Cycle 2, and at Week 28. Pain assessments will be halted at the patient's request or if the patient discontinues study treatment for reasons other than disease progression.

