## 6.5 Duration of Follow-Up

Patients will be followed every 2 weeks during treatment (16 weeks), then every 4 weeks until Week 28, and then every 3 months or as clinically indicated for 12 months after the first Sn-117m-DTPA dose or until death, whichever occurs first. After the 1-year follow-up period, dates of death will be collected for all patients until the final patient completes his 1-year follow-up. Patients removed from study for unacceptable adverse event(s) will be followed until resolution or stabilization of the adverse event.

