## 9.4 Analysis of Secondary Endpoints

Secondary endpoints will be summarized depending on data type. Categorical endpoints will be summarized by frequency and percent. Continuous variables will be summarized by mean and standard deviation at each assessment time point. Time-to-event endpoints will be summarized by Kaplan-Meier Methods. Safety and toxicity will be assessed through the frequency and percent of adverse events (AEs), serious adverse events (SAEs), and adverse events of special interests (AESIs). Toxicity will be assessed using Common Terminology Criteria for Adverse

Events v 5.0 (CTCAE). Safety and toxicity will also be assessed by patient-reported outcomes and adverse events (PRO-CTCAE) captured by digital instruments during treatment and 8 weeks after the last injection to monitor for acute toxicity and every 2-4 weeks for 6 months post-therapy for monitoring of long-term toxicity. CTCAE grades for the corresponding time period will be presented in conjunction with PRO-CTCAE scores. PSA and ALP response rates will be calculated for each of the above defined categories with the corresponding confidence intervals. *Post-hoc* analysis on PSA and ALP levels may be conducted to explore possible trends in PSA and ALP levels. Time to the first symptomatic skeletal event will be analyzed using the Kaplan-Meier method. Estimation and confidence intervals for the median time to first symptomatic skeletal event will be provided. Patients who did not have a symptomatic skeletal event will be censored at the last study visit. PFS will be analyzed in a similar manner as the time to first skeletal event. Patients who did not have observed clinical progression will be censored at the last assessment.

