#### 9.4.9 Overall Survival

OS will be calculated from the time of the first study treatment until the date of death. OS data will be censored if death is not observed.

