## 11. STUDY CALENDAR

Baseline evaluations are to be conducted within 4 weeks prior to start of protocol therapy. Scans and x-rays must be done  $\leq$  8 weeks prior to the start of therapy. In the event that the patient's condition is deteriorating, laboratory evaluations should be repeated within 48 hours prior to initiation of the next cycle of therapy.

Visit dates and scans can be within  $\pm$  7 days of planned dates. Study treatment must start within 30 days of registration.

	Pre-study	Cycle 1 (8 weeks or 56 days)					Cycle 2 (8 weeks or 56 days)					Post-treatment					Follow-up a	Off-study visit	
		W1	W2	W4	W6	W8	W1	W2	W4	W6	W8	18 weeks	20 weeks	22 weeks	24 weeks	26 weeks	28 weeks		
Sn-117m-DTPA		A					A											A*	
Informed consent	X																		
Demographics	X																		
Medical History	X																		
Pain medication**	X	X	X	X	X	X		X	X	X	X		X		X		X	X (every 3 months)	X
Physical Exam	X	X		X	X			X		X		X		X		X		X	X
Vital signs	X	X		X	X			X		X		X		X		X		X	X
Height	X																		
Weight	X	X		X	X			X		X		X		X		X		X	X
Performance status	X																	X	
CBC/diff, platelets	X	X	X	X	X	X i		X	X	X	X		X		X		X	X	X
Serum chemistry b	X	X	X	X	X	X i		X	X	X	X		X		X		X	X	X
PSA	X			X	X			X		X		X		X		X		X	X
Adverse Events		X-----X																	
Patient-reported pain intensity scale and analgesic use c	X		X	X	X	X		X	X	X	X	X	X	X	X	X	X	X	X
Patient-reported CTCAE d			X	X	X	X		X	X	X	X	X	X	X	X	X	X	X	X
Sn-117m-DTPA dosimetry (optional) e		X	X	X	X														
Urine collection for urinalysis f	X						X												

NCI Protocol #: 10437  
 Version Date: January 10, 2022

	Pre-study	Cycle 1 (8 weeks or 56 days)					Cycle 2 (8 weeks or 56 days)					Post-treatment					Follow-up a	Off-study visit	
		W1	W2	W4	W6	W8	W1	W2	W4	W6	W8	18 weeks	20 weeks	22 weeks	24 weeks	26 weeks	28 weeks		
Radiologic evaluation (CT of abdomen/pelvis and bone scan) and chest X-ray g or PSMA PET CT scan	X					X					X				X			X (every 3 months)	
Research blood for genomic whole exome sequencing (mandatory when archival tissue or slides are submitted)	X																		
Research blood for exploratory studies (optional) h	X					X h					X h				X				
Archival tissue for genomic sequencing and exploratory PLK1 stain (optional)	X																		

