#### 12.2.6 Progression-Free Survival

PFS is defined as the duration of time from start of treatment to time of progression or death, whichever occurs first.

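### PFS is defined in two incompatible ways: Section 9 counts only progression, from enrollment; Section 12.2.6 counts progression or death, from start of treatment; nothing says which governs.

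*Combined protocol and SAP*

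**What the plan says.** Objective 1.2.9 names PFS once, alongside OS, among the secondary objectives. Three places then specify it.

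- **Section 9.4** uses the plain label PFS, analyses it by Kaplan-Meier in the manner of time to first skeletal event, and adds: "Patients who did not have observed clinical progression will be censored at the last assessment".
- **Section 9.4.8** calls it clinical PFS and runs it from study enrollment to disease progression. The listed events are symptomatic progression (increasing pain from a metastatic lesion), bone progression by PCWG3 and soft-tissue progression by RECIST v1.1. Then: "Clinical PFS will be censored if clinical progression is not observed". No censoring date is given, and death is not mentioned.
- **Section 12.2.6**: "PFS is defined as the duration of time from start of treatment to time of progression or death, whichever occurs first".

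For comparison, Section 9.4.9 states: "OS will be calculated from the time of the first study treatment until the date of death". On the gap between the two PFS origins, the study calendar in Section 11 states: "Study treatment must start within 30 days of registration". Section 4.4 gives the same 30-day limit.

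**The concern.** The two definitions give different results from the same data in two respects.

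**Event set.** A patient who dies with no recorded progression is an event at death under Section 12.2.6. Under Sections 9.4 and 9.4.8 the same patient is censored at the last assessment. Censoring treats the death as if the patient could still progress later, so the resulting curve describes time to progression although it carries the PFS label.

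**Time origin.** Section 9.4.8 starts at enrollment. Section 12.2.6 and OS start at treatment. Under Section 9, PFS and OS from the same trial would run on different clocks.

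Such deaths can arise under the plan. Section 12.2.4.3 provides for general health decline that ends treatment without objective progression, and this is not a listed Section 9.4.8 event unless pain increases. Section 5.10.2.2.2 halts pain assessments "if the patient discontinues study treatment for reasons other than disease progression", which removes one route by which progression would be recorded before death.

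At stake is the reading of one descriptive secondary endpoint. A reader of the results could not tell which definition was used, and the choice could be made after the data are seen.

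**Working it through.** The plan states no PFS median, event count or power, so there is no figure to reproduce. The check is a comparison of the texts, then an illustration of size.

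**1. Side by side**

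| | Sections 9.4 and 9.4.8 | Section 12.2.6 |
|---|---|---|
| Origin | enrollment | start of treatment |
| Events | progression (three types) | progression or death |
| Death without recorded progression | censored (9.4: last assessment; 9.4.8: no date) | event at death |

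**2. Exact check, one death.** Take n = 25 (Section 9.2) and assume complete follow-up to Month 6, with 12 first events by then, one of them a death without progression.
- Death counted: (25 − 12)/25 = 13/25 = 52.0%.
- Death censored before any of the 11 progressions: 13/24 = 54.2%.
- Death censored after all 11 progressions: 14/25 = 56.0%.

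The estimate therefore rises by 2.2 to 4.0 points when the death falls before Month 6.

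**3. Simulation.** Assumptions: 25 exponential first-event times; follow-up cut at 52 weeks (Section 6.5); k of the first events within 52 weeks chosen at random to be deaths without progression; scans at Weeks 0, 8, 16, 24, 36 and 48 (the frequency in Section 12.1.1); 4,000 runs per setting. Rule A counts the death. Rule B censors it at the last scan. Kaplan-Meier estimate at Week 26, true median 6 months:

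| k | Rule A | Rule B | Mean gain (points) | 5th to 95th percentile | B lower than A |
|---|---|---|---|---|---|
| 1 | 50.0% | 51.7% | +1.65 | −0.3 to +3.6 | 7% of runs |
| 2 | 50.2% | 53.6% | +3.39 | 0 to +6.5 | 4% |
| 3 | 49.8% | 55.0% | +5.21 | +1.5 to +9.3 | 1% |

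Repeat simulations agreed to about 0.1 point. With k = 0 the curves coincide apart from the origin. The mean gain is smaller than in step 2 because some of the deaths fall after Week 26. Rule B is occasionally lower because a patient censored at the last scan leaves the risk set before the date of death.

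**4. Sensitivity.** With true medians of 4 to 9 months and either the last scan or the last pain report as censoring date, the mean gains are +1.4 to +2.0 (k = 1), +3.0 to +3.9 (k = 2) and +4.5 to +6.0 (k = 3). If the deaths are spread over all follow-up with no 12-month cut, the Rule B value is 0.50^(1 − d), where d = k/25 is the share of first events that are such deaths. For d = 0.04, 0.08 and 0.12 this gives 51.4%, 52.9% and 54.3%, or gains of +1.4, +2.9 and +4.3.

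**5. Scale of sampling error.** At 50% with n = 25 the standard error is √(0.5 × 0.5/25) = 0.10, or 10 points.

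**6. Origin.** Taking enrollment as registration, the enrollment origin adds 0 to 30 days to each patient's time. The maximum is 30/30.44 = 0.99 month.

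**The case against.** **Clinical PFS in 9.4.8 and PFS in 12.2.6 could be two endpoints.** This does not stand. Section 9.4 applies the progression-only censoring rule under the plain label PFS, objective 1.2.9 lists one PFS, and Section 9 contains no analysis of a second.

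**Section 9.4.8 may only say which progressions count, with 12.2.6 supplying death as an event.** This has weight. A reader might infer from Section 9 that the sponsor has settled on a time-to-progression analysis reported as PFS. The documents do not support that, because a death-inclusive definition is also in force. What is shown is an unreconciled definition. The harmonising reading is itself not written down, and the censoring sentences in 9.4 and 9.4.8 contradict it if followed as they stand.

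**Few deaths may be affected.** This also has weight. Increasing pain is itself an event and is reported every 2 weeks to Week 28 (Section 5.10.2.2.2). Halting pain reports does not halt imaging. Section 12.2.4.3 asks sites to keep trying to document progression after treatment stops. Section 10.3.3 asks for evidence of progression when a death is attributed to disease, although that does not make the death a Section 9.4.8 event. A reader might also project a number of affected deaths from the fatal SAEs in the earlier randomized study (Section 2.2.4.2). That is not supported: whether those patients had progressed, and how long they were followed, is not stated.

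**The effect is small beside sampling error.** True for one death: 1.7 points against a standard error of about 10. But the shift is on average in the drug's favour, and a larger sample would not remove it.

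**Conclusion.** The point holds as an unresolved contradiction. Sections 9.4 and 9.4.8 differ from Section 12.2.6 in both event set and time origin, and nothing says which governs. Applying Section 9 literally censors deaths without recorded progression and on average raises the PFS curve.

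The size is conditional. Under an assumed 6-month median with 25 patients it is about +1.7, +3.4 and +5.2 points at 6 months for one, two or three such deaths. It is zero if there are none, which is possible. The median, the number and timing of deaths and the scan schedule are assumptions; Section 11 leaves the follow-up scans partly to clinical indication and institutional practice, so actual dates may be less regular. The origin difference of up to 30 days applies however many deaths occur.

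PFS is descriptive here, with no test or threshold attached. The primary endpoint and its decision rule are unaffected. The correction should still be made before analysis, so that the definition cannot depend on the results.

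**What to change.** Use one definition in Sections 9.4 and 9.4.8, for example:

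*PFS is the time from first Sn-117m-DTPA injection to clinical progression (as listed in 9.4.8) or death from any cause, whichever is first. Patients alive without progression are censored at the last disease assessment at which they were known to be free of progression (imaging or, for symptomatic progression, pain assessment).*

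This agrees with Section 12.2.6 and with the OS origin. Allowing pain assessments as well as imaging keeps the censoring date consistent with the 9.4.8 event list; an imaging-only date would discard observed event-free time. Starting at first injection excludes no analysed patient, because the efficacy population in Section 9.6.2 is drawn from patients who received at least one dose.

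Two related items:
- Time to first symptomatic skeletal event (Section 9.4.3) also starts at enrollment. State whether that is intended once PFS starts at treatment.
- If the progression-only endpoint is also wanted, report it separately as *time to clinical progression*.

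Cost: two sentences of analysis text and no new data. Injection, imaging and pain-assessment dates are already recorded, and Section 6.5 provides for the rest: "After the 1-year follow-up period, dates of death will be collected for all patients until the final patient completes his 1-year follow-up". The downside is that reported PFS may be slightly less favourable.

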#### 9.4.9 Overall Survival

OS will be calculated from the time of the first study treatment until the date of death. OS data will be censored if death is not observed.

### 9.5 Analysis of Exploratory Endpoints

#### 9.5.1 Tumor Genomic Alterations

#### 9.5.2 Changes in Systemic Inflammatory Markers and Immune Cell Populations

#### 9.5.3 PLK Immunohistochemistry

Immunohistochemistry for PLK1 will be performed using a PLK1 mouse monoclonal antibody manufactured by Sigma Aldrich (Cat#05-844). Staining will be performed on 5-micron sections obtained from formalin-fixed, paraffin-embedded tissue, with the appropriate antigen retrieval method, blocking step, and dilution as recently determined (manuscript in submission). PLK1 will be scored utilizing a modified Quickscore Method as follows:

Intensity	Score
No staining	0
Light staining	1
Moderate staining	2
Strong staining	3
Proportion	Score
0-4%	1
5-20%	2
21-40%	3
41-60%	3
61-80%	5
81-100%	6

Expression Scores will be calculated as Intensity Score  $\times$  Proportion Score and classified as one of three score tiers:

- Low Expression: 1-3
- Moderate Expression: 3-5
- High Expression:  $\geq 6$

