1.3.2 To examine the changes in systemic inflammatory markers (such as interferon [IFN]-

gamma, tumor necrosis factor [TNF]-alpha, interleukins [IL]-8, IL-10, and IL-17) by flow cytometry, and changes in markers of immune function by measuring the percentage and absolute number of CD4+ T helper cells, CD8+ T cytotoxic cells, T regulatory cells, polymorphonuclear (PMN) myeloid-derived suppressor cells (MDSCs), and mononuclear MDSCs (M-MDSCs) prior to treatment *vs.* end of cycle 1, end of cycle 2, and at week 24 and correlate values and/or changes with treatment outcomes.

1.3.3 To evaluate the feasibility of measuring polo-like kinase 1 (Plk1) expression via immunohistochemistry (IHC) staining on archival tissues.

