## 2.4 Correlative Studies Background

### 2.4.1 Whole Exome Sequencing (WES)

**Biologic Rationale:** Gene expression profiling is an important tool to elucidate the novel biomarkers of radio-sensitivity in order to predict treatment response. Radiation induces DNA damage and thus causes cell death. Upregulation of DNA damage response pathways was associated with radiation sensitivity (Kamran and Mouw, 2018). Extent of somatic copy number alterations and increased expression of PI3K and JAK/STAT pathway components were associated with radiation resistance.

**Hypothesis:** We propose to test for DNA damage repair (DDR) gene alterations (*BRCA1/2* loss/mutation, *ATM*, *ATR*, *CHEK1/2* loss/mutation, *RAD50*, *PALB2*, *CDK12*, *FANCA*, *POLE* mutation), somatic mutations in MMR genes (*MLH1*, *MSH2*, *MSH6*, *PMS2*), replication stress

(*CCNC1*, *CCNE1*, *MYCN* amplification) and *TP53*, *PIK3CA*, *FBXW7*, and *KEAP1* mutations and will correlate with treatment outcomes. Additionally, we propose to test for germline variants such as *MLH1*, *MSH2*, *MSH6*, *PMS2* (for Lynch syndrome), and homologous recombination genes such as *BRCA1*, *BRCA2*, *ATM*, *PALB2*, and *CHEK2*. Archival tissue will be employed as available (no new baseline biopsies will be performed).

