#### Statistical Plan:

Correlative endpoints such as systemic inflammatory, immune markers, and expression of PLK and changes from pre- to post-treatment will be summarized using descriptive statistics.

Changes from baseline vs. follow-up time points will be assessed using paired test methodologies. WES data will be processed using the data processing and data analysis pipelines from the Biostatistics and Bioinformatics shared resource of Markey Cancer Center to identify candidate mutated genes with adjustment for false discovery rate.

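### The PLK1 scoring rule cannot give every stained case a single tier: a score of 3 is both Low and Moderate, and a score of 0 has no tier

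*Combined protocol and SAP*

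**What the plan says.** Section 9.5.3 scores PLK1 immunohistochemistry by a modified Quickscore. Intensity scores 0 (none), 1 (light), 2 (moderate) or 3 (strong). Proportion scores 1, 2, 3, 3, 5 and 6 for the bands 0-4%, 5-20%, 21-40%, 41-60%, 61-80% and 81-100%. The expression score is Intensity Score × "Proportion Score and classified as one of three score tiers". The tiers are "Low Expression: 1-3", "Moderate Expression: 3-5" and "High Expression" for scores of 6 or more.

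The Statistical Plan paragraph that closes Section 9.5 groups PLK1 with the blood markers: inflammatory markers, immune markers, "expression of PLK and changes from pre- to post-treatment will be summarized using descriptive statistics". It then adds: "Changes from baseline vs. follow-up time points will be assessed using paired test methodologies". Neither sentence makes an exception for PLK1.

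Elsewhere PLK1 comes from one source. Objective 1.3.3 concerns the feasibility of "immunohistochemistry (IHC) staining on archival tissues". Section 2.4.3 places the measurement before radiotherapy. The Section 5.8 biomarker table lists the specimen as archival and optional, and Section 5.9.2.1 describes only archival slides or sections cut from archival blocks. Section 5.2, on research biopsies, is marked not applicable.

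**The concern.** A classification rule should send each possible result to exactly one class. Here the two lower tiers share an endpoint and the lowest attainable score lies outside all three. Two people applying the rule exactly as printed could file the same slide differently, and an unstained slide could not be filed at all. The repeated 3 in the proportion scale also makes 21-40% and 41-60% indistinguishable.

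The stake is modest. Section 5.8 gives the purpose of the assay as evaluating how well it predicts response to therapy, and Section 2.4.3 says the results will guide later biomarker work. Enrolment is at most 25, tissue is optional, and the trial is open-label. If the tier for a score of 3 is chosen after outcomes are known, even one or two cases could visibly alter a three-row table.

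The second issue is that, read literally, the statistical plan asks for a PLK1 change over time and a paired test, for which no patient will have a second value.

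**Working it through.** **Inputs**, all from Section 9.5.3: intensity 0, 1, 2, 3; proportion points 1, 2, 3, 3, 5, 6; tiers Low 1-3, Moderate 3-5, High 6 or more. Score = intensity × proportion points. The plan states no figure to reproduce here, so the check is a full enumeration: 4 × 6 = 24 combinations.

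| Intensity | 0-4% (1) | 5-20% (2) | 21-40% (3) | 41-60% (3) | 61-80% (5) | 81-100% (6) |
|---|---|---|---|---|---|---|
| None (0) | 0 no tier | 0 no tier | 0 no tier | 0 no tier | 0 no tier | 0 no tier |
| Light (1) | 1 Low | 2 Low | 3 Low and Moderate | 3 Low and Moderate | 5 Moderate | 6 High |
| Moderate (2) | 2 Low | 4 Moderate | 6 High | 6 High | 10 High | 12 High |
| Strong (3) | 3 Low and Moderate | 6 High | 9 High | 9 High | 15 High | 18 High |

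**Count as printed.** No tier 6; Low only 3; Low and Moderate 3; Moderate only 2; High 10. The total is 6 + 3 + 3 + 2 + 10 = 24. Exactly one tier: 3 + 2 + 10 = 15.

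**Realistic cells.** The lowest proportion score is 1, so a product of 0 arises only from intensity 0. If proportion means the share of stained cells (an assumption; the section does not define it), no staining can realistically pair only with 0-4%. That leaves 18 stained cells plus 1 negative cell = 19, of which 3 + 1 = 4 lack a unique tier (4/19 = 21%, against 9/24 = 38% for the full grid). Neither percentage is a share of patients, because the documents give no distribution of scores.

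**Effect of the repeated 3.** Suppose, as an assumption only, that 41-60% should score 4.
- Light × 41-60% moves from 3 (two tiers) to 4 (Moderate).
- Moderate × 41-60% moves from 6 to 8, and strong × 41-60% from 9 to 12; both stay High.
- Two cells still score 3 (light × 21-40% and strong × 0-4%), and the six zero cells still have no tier.

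The repeated value therefore merges two bands and can change a tier only at light intensity. The overlap and the gap at 0 exist whatever the 41-60% value is.

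**Number of PLK1 time points.** Archival tissue is the only PLK1 source in Objective 1.3.3 and Sections 5.1, 5.5.1, 5.8 and 5.9.2.1. Section 2.4.3 puts the measurement before treatment, and Section 5.2 provides for no research biopsies. Post-treatment PLK1 values per patient: 0, so a within-patient PLK1 change cannot be computed.

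**The case against.** The best case for leaving this alone is that PLK1 is exploratory, optional and third in tissue priority, and touches no decision in the trial. Most combinations (15 of 24) classify without difficulty. Section 9.5 plans only descriptive statistics for PLK1 and specifies no PLK1-by-outcome analysis that could be biased. All of this is correct, and it sets the weight of the point. It does not remove the contradiction: no other section says where 3 or 0 belongs.

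The pre-to-post sentence can also be read charitably, with PLK1 expression summarised once and changes applying only to the serially sampled blood markers. Objective 1.3.2 supports that reading, since it limits the change objective to inflammatory and immune markers. This stands. The wording is loose, and one clarifying clause is all it needs.

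Three stronger readings are tempting, and the documents do not support them:
- A reader might infer that the score is unusable, or that 38% of patients could not be classified. The 38% counts table cells, most of them unrealistic zero-score cells.
- A reader might infer that the feasibility objective fails unless every case has a tier. Objective 1.3.3 and Section 2.4.3 concern whether PLK1 can be measured, and neither defines feasibility by tier.
- A reader might infer that 41-60% was certainly meant to score 4. The sequence suggests it, but the method is described as modified and no source for its points is given.

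Nor should the remark in Section 2.4.1 that "no new baseline biopsies will be performed" carry the baseline-only argument. It sits in the exome-sequencing section and speaks only of baseline tissue; Section 5.2 is the relevant support.

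**Conclusion.** The rule in Section 9.5.3 is inconsistent as written. It gives two tiers to a score of 3 (light × 21-40%, light × 41-60%, strong × 0-4%) and none to a score of 0. These conclusions follow from the printed points and bounds alone. The duplicated 3 for 41-60% is a probable but unconfirmed misprint. How many patients are affected cannot be estimated from the documents. Section 5.5.1 accepts PLK1 tissue up to two decades old, which makes weak or absent staining plausible, but that is an inference and not a stated fact.

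The single time point for PLK1 is clear from the specimen sections; only the statistical plan fails to say so. Overall this is a minor drafting correction, worth making before any PLK1 result is read against outcome.

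**What to change.** In Section 9.5.3:
- Check the 41-60% points against the assay method and correct them if they are misprinted.
- Set mutually exclusive tiers that cover every attainable score, including 0. One option is Low 0-3, Moderate 4-5, High 6 or more. With the printed points this places 12 + 2 + 10 = 24 cells; with 41-60% scored 4 it places 11 + 3 + 10 = 24. Another option is a separate Negative tier for 0, in which case the reference to three tiers must also change. The choice belongs to the sponsor and the assay laboratory.
- Fix the tiers before any PLK1 result is linked to outcome, and report the raw score alongside the tier.

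In the Statistical Plan paragraph of Section 9.5, state that PLK1 is measured once, on archival tissue, and that pre-to-post changes and paired tests apply only to the serially sampled blood markers.

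The cost is a few words in two places. No extra tissue, staining or patient burden is involved.
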